6.12.3. Deaths, Other Serious Adverse Events, and Other Notable Adverse Events

The number and percentage of patients who experienced a serious adverse event during the treatment period will be summarized by treatment using MedDRA Preferred Term nested within System Organ Class. Events will be ordered by decreasing frequency within System Organ Class.

These summary tables will be generated for the Induction and Maintenance Periods and for All Periods.

In the event differential dropout rates are seen or to further investigate serious events of interest, summary tables comparing exposure-adjusted incidence rate (that is, person-time-adjusted incidence rates) over the entire time period will be generated for the Induction and Maintenance Periods.

A listing of deaths will be provided. All deaths will be included, regardless of the Investigator's or the Sponsor's judgment about causality, including (1) any deaths occurring during participation of the study, (2) any deaths occurring after a patient leaves (that is, discontinued from the study or completes the study if the death is the result of a process initiated during the study, regardless of when it actually occurs. Each listing will include investigator ID, patient ID, treatment group, baseline age, sex, associated AE, whether or not the death and Lilly's assessment of whether the process leading to death (NOT the death itself) began:

- a) “On study”: during study or within the 24-hour day after date of discontinuation or completion.
- b) “Shortly after study”: from the end of the time period in a) to 4 weeks after date of discontinuation or completion or
- c) “Long after study”: more than 4 weeks (or longer, as specified in b) after the date of discontinuation or completion.

6.12.4. Clinical Laboratory Evaluation

Laboratory evaluations will be summarized and analyzed for the Induction Period only except where noted.

Laboratory tests include all planned analytes as defined in the protocol, excluding those collected in a reflex manner (only collected under certain circumstances).

Values at each visit (starting at randomization) and change from baseline to each visit for laboratory tests will be displayed in box plots (notched box for each treatment with outliers displayed) for patients who have both a baseline and a result for the specified visit. Individual measurements outside of reference limits will also be displayed using distinct symbols overlaying the box plot. Baseline will be the last non-missing observation in the baseline period. Original-scale data will be used for the display. Unplanned measurements will be excluded. Displays using both SI and U.S. conventional units will be provided (when different). The following summary statistics will be included in a table below the box plot: N, mean, standard deviation, minimum, Q1, median, Q3, and maximum. P-values and confidence limits will not be included in the summary statistics at the bottom of the box plot. Box plots will be used to evaluate trends over time and to assess a potential impact of outliers on central tendency summaries.

Change from baseline to last observation will also be summarized within the box plot of changes (rightmost column) for patients who have both baseline and at least 1 postbaseline result. Baseline will be the last nonmissing observation in the baseline period. The last nonmissing observation in the treatment period will be used as the last observation. Original-scale data will be used. Unplanned measurements will be excluded.

For quantitative laboratory analyte measurements, 3-panel displays that include a scatterplot, a shift table, and a shift to high/low table will be created. Specifically, for each measurement, both a 3-panel display assessing low values and a 3-panel display assessing high values will be created.

In the 3-panel display to assess low values, the scatterplot will plot the minimum value during the baseline period versus the minimum value during the treatment period. Lines indicating the reference limits are included. In cases where limits vary across demographic characteristics, lines indicating the most common limit will be displayed. The shift table will include the number and percentage of patients within each baseline category (minimum value is low, normal, high, or missing) versus each treatment category (minimum value is low, normal, or high) by treatment. Patients with at least 1 result in the treatment period will be included in the

shift table. The shift from normal/high to low table will include the number and percentage of patients by treatment whose minimum baseline result is normal or high and whose minimum treatment result is low. Patients whose minimum baseline result is normal or high and have at least 1 result during the treatment period are included. The Fisher's exact test will be used to compare percentages of patients who shift from normal/high to low between treatments.

The 3-panel display to assess high values will be created similarly. The scatterplot will plot the maximum value during the baseline period versus the maximum value during the treatment period. The shift table will include the number and percentage of patients within each baseline category (maximum value is low, normal, high, or missing) versus each treatment category (maximum value is low, normal, or high) by treatment. The shift from normal/low to high table will include the number and percentage of patients by treatment whose maximum baseline result is normal or low and whose maximum treatment result is high. Patients whose maximum baseline result is normal or low and have at least 1 result during the treatment period are included. The Fisher's exact test will be used to compare percentages of patients who shift from normal/low to high between treatments.

The low/high displays will be created for the Maintenance Period as well, but no statistical comparisons are planned and only summaries will be produced.

For laboratory analyte measurements collected qualitatively, a listing of abnormal findings will be created. The listing will include patient ID, treatment group, laboratory collection date, analyte name, and analyte finding.

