**10.3.4. Safety Analyses**

Safety will be assessed by evaluating AE, laboratory analytes, vital signs, ECGs, and C-SSRS.

The induction period safety analyses will compare LY3074828 to placebo for which treatment group comparisons will be analyzed using the methods described in Section 10.3.1.1. The maintenance period safety analyses will summarize safety measures by treatment. Summaries of safety data collected during the follow-up period will be presented separately.

AEs will be coded according to the *Medical Dictionary for Regulatory Activities* and summarized by system organ class, preferred term, severity, and relationship to investigational product. A treatment-emergent adverse event (TEAE) is defined as an event that first occurred or worsened in severity after baseline. For each event classification term, the number of subjects experiencing a TEAE with that classification term will be tabulated.

Treatment-related TEAEs are defined as events that are indicated by the investigator on the eCRF to be related to treatment. If a subject reports the occurrence of a particular event more than once, the most severe of those events will be included in the summary tables of TEAEs, and the most severe of the most related of those events will be included in the summary tables of

treatment-related events. For events that are gender specific, the denominator and computation of the percentage will only include subjects from the given gender.

Additional safety parameters include laboratory analytes, vital signs, ECGs, and C-SSRS. Laboratory analytes and vital signs will be presented as mean changes from baseline and as incidence of abnormal values. ECG and C-SSRS data will be listed by subject. Other covariate data, including body weight, will be summarized by treatment group.

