5.1. Summary of Study Design

Study AMAF is a multicenter, randomized, parallel-arm, placebo-controlled trial with 4 study periods in subjects with moderate-to-severe plaque psoriasis.

[figure not shown]
Screening Period (≤4 weeks): Subjects will be evaluated for study eligibility ≤28 days before the baseline visit (Visit 2/Week 0). At the baseline visit (Visit 2), subjects who fulfill the eligibility criteria will be randomized to 1 of 4 induction treatment arms.

Induction Period (16 weeks): A double-blind, 16-week Induction Period is designed to establish the efficacy and safety of LY3074828 administered at Visit 2 (Week 0) and Visit 5 (Week 8). Subjects will be randomized to 1 of 4 induction treatment arms (LY3074828 30 mg SC, LY3074828 100 mg SC, LY3074828 300 mg SC, and placebo every 8 weeks [Q8W]) stratified on the basis of previous exposure to biologic therapy for treatment of psoriasis.

Maintenance Period (88 weeks): The Maintenance Period consists of 88 weeks of treatment. At the end of the Induction Period (Week 16), subjects will continue treatment in the Maintenance Period which is intended to explore 1 of 2 treatment strategies through Week 104. All placebo subjects and subjects assigned to treatment with LY3074828 who have a <90% improvement in Psoriasis Area and Severity Index (PASI) from baseline (PASI 90) at Week 16 will receive LY3074828 300 mg SC Q8W during the entire Maintenance Period. Subjects with ≥PASI 90 PRN dosing group) at Week 16 will only be dosed with LY3074828 at the baseline dose level assignment no more frequently than Q8W when disease activity level is <PASI 90, and this will continue until ≥PASI 90 is regained.

Follow-up Period (16 weeks): The Follow-up Period will include a visit every 4 weeks for a total of 16 weeks following Visit 29 to assess subject safety and study drug efficacy.

[Figure 5.1](#) illustrates the study design.

^a Visits will occur every 4 weeks in the Maintenance and Follow-up Periods.
 Abbreviations: PASI = Psoriasis Area and Severity Index; PRN = as needed; Q8W = every 8 weeks.

Figure 5.1. Illustration of study design for Clinical Protocol I6T-MC-AMAF.

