5.2. Determination of Sample Size

Approximately 200 subjects will be randomized at a 1:1:1:1 ratio in the blinded induction dosing period to LY3074828 30 mg, 100 mg, 300 mg, and placebo (50 subjects per dosing regimen, respectively). Randomization will be stratified by prior exposure to biologic therapy for psoriasis (yes/no).

Assuming 60% and 3% PASI 90 response rates at 16 weeks for LY3074828 and placebo, respectively, pairwise comparisons to placebo have over 99% power using a 2-sided Fisher's exact test at the 0.05 significance level, with no adjustment for multiple comparisons.

As results for PRN dose arms in the Maintenance Period will support the maintenance dosing strategy in Phase 3 planning, a reasonable total number of subjects who completed 1-3 visits in the Maintenance Period (Week 20 to Week 28) will be needed. Based on study simulations under the treatment effect scenario outlined above, approximately 49 subjects (9 on 30 mg, 18 on 100 mg, 22 on 300 mg PRN arms) will have completed the Week 20 visit at the time of the primary endpoint datalock.

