6.12.1. Extent of Exposure

6.12.1.1. Duration of Exposure

Duration of exposure to study treatment (defined as time since first injection of study treatment in days) will be summarized by treatment group during the Induction Period, the Maintenance Period, and the combined Induction Period, Maintenance Period, and Rescue Period.

Duration of exposure during the Induction Period will be calculated as:

$$(Date\ of\ last\ study\ visit\ in\ the\ Induction\ Period - Date\ of\ first\ injection\ of\ study\ treatment + 1)$$

Duration of exposure during the Maintenance Period will be calculated as:

$$(Date\ of\ last\ study\ visit\ in\ Maintenance\ Period - Date\ of\ last\ study\ visit\ in\ the\ Induction\ Period + 1)$$

Duration of exposure during the Rescue Period will be calculated as:

$$(Date\ of\ last\ study\ visit\ in\ Rescue\ Period - Date\ of\ First\ Rescue\ Treatment + 1)$$

Duration of exposure to LY3074828 for the combined Induction Period, Maintenance Period, and Rescue Period will be calculated as:

$$(Date\ of\ last\ study\ visit\ in\ the\ Maintenance\ Period - Date\ of\ first\ injection\ of\ LY3074828 + 1)$$

for subjects without rescue and

$$(Date\ of\ last\ study\ visit\ in\ the\ Rescue\ Period - Date\ of\ first\ injection\ of\ LY3074828 + 1)$$

for subjects with rescue

For the combined Induction Period, Maintenance Period, and Rescue Period summaries, exposure will be summarized for all LY3074828 dosing regimens pooled.

Descriptive statistics will be provided for patient days of exposure and the frequency of patients falling into the following different exposure ranges (that is, only the exposure ranges that fall within the treatment period will be presented) will be summarized:

- >0, ≥7 days, ≥14 days, ≥30 days, ≥60 days, ≥90 days, ≥120 days, ≥183 days, ≥365 days, ≥548 days.
- >0 to <7 days, ≥7 to <14 days, ≥14 to <30 days, ≥30 to <60 days, ≥60 to <90 days, ≥90 to <120 days, ≥120 to <183 days, ≥183 to <365 days, ≥365 days to <548 days, and ≥548 days.

Additional exposure ranges may be considered if necessary.

A by-patient listing of exposure duration will be provided.

No inferential analysis for comparison between treatment arms will be performed.

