6.12.4.1. Hepatic Laboratory Examinations

Analyses for change from baseline to last observation, change from the minimum value during the baseline period to the minimum value during the treatment period, change from the maximum value during the baseline period to the maximum value during the treatment period, and treatment-emergent high or low laboratory results at any time are described in Section 6.12.4. This section describes additional analyses for the topic.

The percentages of patients with the following elevations in hepatic laboratory tests at any time will be summarized between treatment groups:

- The percentages of with a alanine aminotransferase (ALT) measurement greater than or equal to 3 times (3X), 5 times (5X), and 10 times (10X) the Covance upper limit of normal (ULN) during the treatment period will be summarized for all patients with a postbaseline value and for subsets based on various levels of baseline.
 - The analysis of 3X ULN will contain 4 subsets:
 - patients whose non-missing maximum baseline value is less than or equal to 1X ULN,
 - patients whose maximum baseline is greater than 1X ULN but less than 3X ULN,

- patients whose maximum baseline value is greater than or equal to 3X ULN, and
- patients whose baseline values are missing.
- The analysis of 5X ULN will contain 5 subsets:
 - patients whose non-missing maximum baseline value is less than or equal to 1X ULN,
 - patients whose maximum baseline is greater than 1X ULN but less than 3X ULN,
 - patients whose maximum baseline is greater than or equal to 3X ULN but less than 5X ULN,
 - patients whose maximum baseline value is greater than or equal to 5X ULN, and
 - patients whose baseline values are missing.
- The analysis of 10X ULN will contain 6 subsets:
 - patients whose non-missing maximum baseline value is less than or equal to 1X ULN,
 - patients whose maximum baseline is greater than 1X ULN but less than 3X ULN,
 - patients whose maximum baseline is greater than or equal to 3X ULN but less than 5X ULN,
 - patients whose maximum baseline is greater than or equal to 5X ULN but less than 10X ULN,
 - patients whose maximum baseline value is greater than or equal to 10X ULN, and
 - patients whose baseline values are missing.

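### By default the SAP's ALT, AST and bilirubin threshold tables cover Induction only, so 88 of 104 planned treatment weeks have no threshold counts

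*SAP*

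**What the plan says.** - **Default.** SAP 6.12.4: "Laboratory evaluations will be summarized and analyzed for the Induction Period only except where noted".
- **Exception for laboratory tables.** The same section extends the low/high displays to Maintenance, as summaries without testing. For each quantitative analyte these have three panels: a scatterplot of baseline against on-treatment extremes with reference-limit lines, a shift table, and a shift-to-high (or low) table.
- **Reduced set.** SAP 6.12 plans a smaller safety set for Maintenance and for the pooled LY3074828 summary. Treatment-emergent high/low results are the laboratory example in both.
- **Hepatic tables.** SAP 6.12.4.1 says that the percentages of patients with specified "elevations in hepatic laboratory tests at any time will be summarized between treatment groups". It refers to the treatment period but names neither Maintenance nor All Periods.
- **Profiles.** The same section plans individual graphic profiles, in any phase, for ALT or AST ≥5X ULN or ALP ≥2X ULN.
- **Protocol.** Section 10.3.4: "The maintenance period safety analyses will summarize safety measures by treatment". It presents laboratory analytes as mean changes and incidence of abnormal values. Section 9.4.5 starts hepatic monitoring at ALT ≥3X, ALP ≥3X or bilirubin ≥2X ULN.

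**The concern.** The hepatic threshold tables are the only planned output that counts subjects by multiple of ULN. If they end at Week 16, they cover the shorter part of the trial. Maintenance is where most exposure accrues, where all placebo subjects first receive LY3074828, and where the 300 mg Q8W group is treated for up to 88 weeks.

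The study report could then give no tabulated count, by treatment group or pooled, of subjects who crossed the protocol's own monitoring levels of ALT ≥3X or bilirubin ≥2X ULN after Week 16. Take a subject at Week 40 with ALT 4X, bilirubin 2.5X and ALP below 2X ULN. That subject would be a point on each analyte's scatterplot and a high in the shift tables, but would be in no threshold table and would trigger no profile.

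**Working it through.** **Which period applies to the hepatic tables**

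1. The default in 6.12.4 governs its subsections unless an exception is noted. 6.12.4.1 notes none for the threshold tables.
2. Wording about any time does not by itself lift the default. SAP 6.12.5 has the same kind of default for vital signs and similar wording for high/low results, yet adds a separate sentence for Maintenance. SAP 6.12.3 names Induction, Maintenance and All Periods for the serious adverse event tables.
3. The term treatment period is not defined in SAP 6.1.2.1. Induction-only is therefore an inference from the default, though the natural one.

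**Share of time left out**

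Inputs: "The Maintenance Period consists of 88 weeks of treatment" (SAP 5.1); Induction is 16 weeks (SAP 5.1); "Approximately 200 subjects will be randomized at a 1:1:1:1 ratio in the blinded induction dosing period" (SAP 5.2), so 150 of 200 start on LY3074828; placebo subjects "will receive LY3074828 300 mg SC Q8W during the entire Maintenance Period" (SAP 5.1). SAP 6.12.1.1 counts exposure as time since first injection, so PRN intervals without a dose count.

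- Plan's figure: 104 − 16 = 88 weeks, which reproduces.
- Planned treatment time after Week 16: 88 / (16 + 88) = 84.6%.
- LY3074828 person-time only, no dropout: 200 × 88 / (150 × 16 + 200 × 88) = 17,600 / 20,000 = 88.0%.
- The documents give no dropout rate. With assumed linear Maintenance dropout d, the mean Maintenance time is 88(1 − d/2) weeks. For d = 10% to 40% the share is 83.9% to 81.5% of all exposure. For LY3074828 exposure alone (mean Induction time 150 × 16 / 200 = 12 weeks) it is 87.4% to 85.4%.

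**Share of chemistry draws left out** (Protocol 2, on-treatment post-baseline serum chemistry)

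- Induction: Weeks 2, 4, 8, 12, 16 = 5.
- Maintenance: Weeks 20 to 52 every 4 weeks (9), then 64, 80, 96, 104 (4) = 13.
- 13 / 18 = 72%.

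**Illustration only: expected cases of ALT ≥3X ULN**

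The rate is an assumption, 1 to 3 per 100 patient-years; the documents give none.

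- Induction: 150 × 16 / 52 = 46 patient-years, so 0.5 to 1.4 expected cases. The chance of none is exp(−1.4) = 25% to exp(−0.5), about 63% with the unrounded mean of 0.46.
- Maintenance: 200 × 88 / 52 = 338 patient-years, or 271 at an assumed 80% average retention, so about 3 to 10 expected cases.

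**What each later output shows**

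| Output after Week 16 | ALT/AST 3X to <5X | Bilirubin ≥2X | ALT/AST ≥5X |
|---|---|---|---|
| Low/high scatterplot | point, no count | point, no count | point, no count |
| Shift and high/low tables | counted only as high | counted only as high | counted only as high |
| Any-phase profiles | not a trigger | not a trigger | individual profile |

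**The case against.** A reader might infer that laboratory data after Week 16 go unanalysed, or that a rise to 4X ULN cannot be told from one to 1.1X. The documents do not support either. The Maintenance displays plot each subject's maximum against the reference limit, so the two values are visibly different. High/low results are also pooled over exposed subjects, and large elevations get profiles. What is missing is the count at each threshold, and any linking of ALT with bilirubin below the profile triggers.

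A reader might also infer that the SAP withdraws threshold tables promised by the protocol. It does not: Protocol 10.3.4 promises mean changes and incidence of abnormal values, and the Maintenance shift tables supply the latter. Protocol 10.3.1 leaves full analysis details to the SAP. The protocol-SAP gap that can be argued is mean change in Maintenance, a separate matter that the fix below does not address.

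Nor does 6.12.4.1 say that its tables are Induction-only. It has rules of its own, such as including unplanned measurements, and the reduced sets in SAP 6.12 are given as examples. This makes the period uncertain, which itself calls for a sentence.

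Other safeguards exist. Protocol 9.4.5 monitoring has no period limit. Clinically significant laboratory findings that lead to a diagnosis are reported as adverse events (Protocol 9.4.3). Treatment-emergent events are summarised for Maintenance (SAP 6.12.2), and blinded review of selected laboratory measurements continues throughout (SAP 6.17). These protect subjects during the trial but do not supply the counts. Maintenance has no placebo arm, so such tables can only be descriptive; they would still be informative.

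**Conclusion.** The point stands as a gap in reporting. Under the SAP's default, the ALT, AST and bilirubin threshold tables omit about 85% of planned treatment time, or 72% of scheduled on-treatment chemistry draws. No other output counts subjects with ALT or AST 3X to <5X or bilirubin ≥2X ULN in that time.

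This rests on reading the default in 6.12.4 as governing 6.12.4.1. If all periods were intended, the same clarifying sentence is needed. The 85% is planned time for a subject who completes Week 104; the dropout range changes it little. The event rates only illustrate scale and are not evidence of a hepatic signal. The change should be made because it affects what hepatic safety the trial can report; the primary analysis is unaffected.

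**What to change.** In SAP 6.12.4.1, state that the ALT, AST and bilirubin threshold tables are produced descriptively for:

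- Induction;
- Maintenance, by the four treatment groups in SAP Table 6.1;
- All Periods LY3074828-exposed subjects, including Rescue.

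Name the baseline that defines the baseline subsets in each. Protocol 10.3.1.2 resets the Maintenance safety baseline to Week 16 for placebo subjects and those without PASI 90, and keeps the pre-randomization value for PASI 90 responders. SAP 6.1.2.2 uses one study baseline before the first injection. The two need reconciling before the subsets can be programmed.

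The cost is a few more tables from existing programs, plus the baseline decision. The data are already scheduled for collection, and no testing is added.
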